6.5 Organ Function Requirements

Dose adjustments for renal insufficiency are recommended according to the Children’s Hospital of Pittsburgh Lexicomp formulary. As existing recommendations for dose adjustment are derived from the adult population and not for pediatric patients, the following table was created to guide participant exclusion based on renal function. The threshold creatinine values in this Table were derived from the Schwartz formula for estimating GFR utilizing child length and stature data published by the CDC.

Table 2. Adequate Pediatric Renal Function:

Adequate renal function defined as:		
- Creatinine clearance or radioisotope GFR \geq 70 mL/min/1.73 m ² or		
- A serum creatinine based on age/gender as follows:		
Age	Maximum Serum Creatinine (mg/dL)	
	Male	Female
1 month to < 6 months	0.4	0.4
6 months to < 1 year	0.5	0.5
1 to < 2 years	0.6	0.6
2 to < 6 years	0.8	0.8

6 to < 10 years	1	1
10 to < 13 years	1.2	1.2
13 to < 16 years	1.5	1.4
≥ 16 years	1.7	1.4

No dose adjustment is needed for hepatic impairment

7. Study Drug Information

7.1 Masking of Study drug

The investigational pharmacy at each trial site will randomize and distribute tranexamic acid or placebo (as an equal volume of normal saline). The manufacturers, batch numbers, and sources will be recorded for all doses. The pharmacy will use the commercially available product purchased for use by the formulary.

Although the investigational pharmacy will be unblinded, they will not share any blinded information with the study team except in case of emergency. Unblinded pharmacy staff will not be involved in patient or outcomes assessment.

Patients, care providers, study coordinators and study investigators will not be told which arm the patient is on. Among study personnel, only the unblinded pharmacists will have access to treatment assignment. The placebo will be normal saline administered by IV. Tranexamic acid in IV solution is clear and colorless and grossly similar to tranexamic acid in appearance. Research coordinators who collect outcomes data will have no contact with study drug.

7.2 Administration of Study Drug

The study drug will be started according to the randomization assignment after meeting activation criteria. The dosing schedule for tranexamic acid will be 10mg/kg every 8 hours (or TID dosing if preferred by primary physician). Tranexamic acid will be diluted in normal saline to a total volume of 15mL. The dosing schedule for placebo will be an equivalent volume of normal saline (15mL) every 8 hours (or TID dosing if preferred by primary physician). Both TXA and placebo will be infused over 15 to 30 minutes, then the line is flushed with normal saline. Nursing staff will be instructed to document in the medical record if medication is not administered within the 15-30 minute infusion time, as well as the reason for this.

Tranexamic Acid does not have Y-site or admixture compatibility with Ampicillin, Blinatumomab, Penicillin or Piperacillin-Tazobactam. Tranexamic acid should not be mixed with blood products. Tranexamic acid may be mixed with most solutions for infusion such as electrolyte solutions, carbohydrate solutions, amino acid solutions and Dextran solutions.

8. Study Procedures and Schedule

The following data will be collected according to the timeline below. If two or more study points fall on the same calendar day (for example if the date of consent and date of randomization are the same day) then all of the unique lab measurements required for

each time point need to be collected, but a lab measurement that is required at both time points does not need to be repeated twice.

8.1 Day of Enrollment

- Thrombotic Assessment
 - Assessment for thrombotic event will be performed via a review of medical chart notes and relevant imaging studies obtained within the time period from prior assessment. This definition of will apply to all future time points when a thrombotic assessment is completed.
- Demographics and Medical History
 - Weight, Height, BMI
 - Date of Birth
 - Gender
 - Ethnicity
 - Race
 - Primary Diagnosis
 - Including disease, current treatment (Radiation, chemotherapy medications, BMT source, Donor ABO Type and Related/Unrelated Donor)
 - ABO Type
 - Concomitant Medications
- Laboratory Assessment (lab studies obtained within 24H period prior to enrollment do not need to be repeated unless otherwise stated)
 - CBC
 - Serum Creatinine
 - Pregnancy Test (Urine or Serum, if female of child-bearing age and >72 hours from previous)
 - HLA Testing results (if done as part of routine care)
 - Coagulation Testing (PT, PTT, INR and Fibrinogen) if PEG-Asparaginase or Erwinia Asparaginase has been given >7 days but ≤14 days from date of enrollment
- Adverse events related to standard anticancer therapies will be carefully monitored for events that would preclude activation of study drug. Collection and documentation of AEs for the trial will begin following first dose of study drug.

8.2 Days Between Enrollment and Randomization; Days Between Randomization and Activation of Study Drug

- Thrombotic Assessment (via chart review), to be completed once weekly
- Laboratory Assessment, to be completed daily
 - CBC
- Adverse events related to standard anticancer therapies will be carefully monitored for events that would preclude activation of study drug. Collection and documentation of AEs for the trial will begin following first dose of study drug.
- Medication Review – Document new or discontinued medications

8.3 Day of Randomization

- Hemostatic/Bleeding Assessment
 - Bleeding will be recorded using the WHO Bleeding score as the bleeding assessment tool. Bleeding assessments will be completed by means of a physical assessment of the patient, patient interview and a review of patient chart and laboratory data for documented bleeding events. Research staff which will be either research nurse, primary investigator or co-investigator, will perform physical assessment of the patient and interview prior to reviewing the patient's medical chart and laboratory data to allow an objective assessment. Nursing staff may provide additional details. If participant has had WHO Grade 2 or higher bleeding within 48H of randomization they will not be randomized. They will be eligible for randomization if bleeding later resolves. This definition of hemostatic/bleeding assessment will apply to all further time points at which a bleeding assessment is completed.
 - If participant has had WHO Grade 2 or higher bleeding within 48H of randomization they will not be randomized. They will be eligible for randomization if bleeding later resolves.
- Thrombotic Assessment (via chart review)
- Laboratory Assessment (lab studies obtained within 24H period prior to randomization do not need to be repeated unless otherwise stated)
 - Coagulation Profile (PT, PTT, INR, Fibrinogen, D-Dimer)
 - CBC
 - Serum Creatinine
 - Pregnancy Test (Urine or Serum, if female of child-bearing age and >72 hours from previous)
 - Urinalysis (if >72 hours from previous)
- Data on Platelet Transfusions
 - Number of platelet units transfused
 - Source of platelet transfusions (apheresis or whole blood)
 - HLA or cross-match compatible
 - Reason for Transfusion
- Data on Red Blood Cell Transfusions
 - Number of units transfused
 - Reason for transfusion
- Adverse events related to standard anticancer therapies will be carefully monitored for events that would preclude activation of study drug. Collection and documentation of AEs for the trial will begin following first dose of study drug
- Medication Review – Document new or discontinued medications

8.4 Day 1 of Study Drug

- Hemostatic/Bleeding Assessment
 - If participant has had Grade 2 or higher bleeding within 48H of initiation of the study drug this should not be activated. They will be eligible for activation of the study drug later if bleeding later resolves.

- Thrombotic Assessment (via chart review)
- Laboratory Assessment (to be drawn prior to first dose of study drug)
 - CBC
 - Serum Creatinine
 - Urinalysis (if >72 hours from last Urinalysis)
 - Fibrinolysis study labs
- Data on Platelet Transfusions
 - Number of platelets transfused
 - Source of platelet transfusions (apheresis or whole blood)
 - HLA or cross-match compatible
 - Reason for transfusion
- Data on Red Blood Cell Transfusions
 - Number of units transfused
 - Reason for transfusion
- Adverse Event Assessment and Reporting – All Grade 3 or greater adverse events will be documented and followed
- Medication Review – Document new or discontinued medications

8.5 Days 2-30 of Study Drug

- Hemostatic/Bleeding Assessment
- Thrombotic Assessment (via chart review)
- Laboratory Assessment
 - CBC – to be drawn daily
 - Serum Creatinine – to be drawn daily
 - Bilirubin level – to be drawn once weekly
 - Fibrinolysis labs – to be drawn on Day 5 (+/- 1 day)
- Data on Platelet Transfusions
 - Number of platelets transfused
 - Source of platelet transfusions (apheresis or whole blood)
 - HLA or cross-match compatible
 - Reason for transfusion
- Data on Red Blood Cell Transfusions
 - Number of units transfused
 - Reason for transfusion
- Adverse Event Assessment and Reporting - All Grade 3 or greater adverse events will be documented and followed
- Medication Review – Document new or discontinued medications

8.6 Day 7 (+/- 3 days) and Day 30 (+/- 3 days) following Discontinuation of Study Drug

- Hemostatic/Bleeding Assessment (via phone conversation or clinic visit for patients who have been discharged; via chart review for patients who remain inpatient)
- Thrombotic Assessment (via phone conversation or clinic visit for patients who have been discharged; via chart review for patients who remain inpatient)

- Adverse Event Assessment and Reporting (via phone conversation or clinic visit for patients who have been discharged; via chart review for patients who remain inpatient). All Grade 3 or greater adverse events will be documented and followed

Table 3. Timeline for Study Assessment

Schedule of Events	Pre-Treatment Period					Treatment Period		Post-Treatment Period
	Pre-Screening	Day of Enrollment ₁	Days Between Enrollment and Randomization	Day of Randomization ₁	Days Between Randomization and Activation	Day 1 of Study Drug	Days 2-30 of Study Drug	
Event								Day 7 (+/- 3 days) and Day 30 (+/- 3 days) after Discontinuation of Study Drug
Medical Chart Review	X							
Informed Consent		X						
Demographics and Medical History		X						
ABO Type		X						
HLA Testing*		X						
Fibrinolysis Labs						X	X ₂	
CBC		X	X	X	X	X	X	
Serum Creatinine		X		X		X	X	
Urinalysis				X ₃		X ₃		
Coagulation Profile (PT/PTT/INR /Fibrinogen/ D-dimer)		X ₄		X				

Pregnancy Test		X ₅		X ₅				
Bilirubin level							X ₆	
Bleeding Assessment				X		X	X	X
Thrombotic Assessment		X	X ₇	X	X ₇	X	X	X
Data on Transfusion				X		X	X	
Drug or Placebo Administered						X	X	
Adverse Event Assessment						ongoing		
Medication Review	ongoing							

1. Lab studies obtained within 24H period prior to enrollment or randomization do not need to be repeated
 2. To be collected at one time point on day 5 (+/- 1 day), at least six hours after administration of the last study drug dose and before the next dose due
 3. Urinalysis does not need to be repeated if within 72 hours of previous.
 4. If patient has received PEG-Asparaginase or Erwinia Asparaginase >7 and ≤14 days from day of enrollment collect PT, PTT, INR and Fibrinogen **only**
 5. Urine pregnancy does not need to be repeated if within 72 hours of previous.
 6. Once weekly while on study drug
 7. To be completed once weekly by chart review
- * If obtained as part of routine care

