3.3 Safety Endpoints

Adverse events and serious adverse events will be monitored and collected from the time of activation of the study drug until a period up to and including 30 days after the last dose of the study drug. Adverse events and serious adverse events will to be assessed by CTCAE v.4.0 criteria and compared between study drug and placebo arms. The following events will specifically be compared across study arms;

- Incidence of thrombotic events (A thrombotic event is defined as venous or arterial thrombosis confirmed on imaging study, which may include Doppler US, CT scan, MRI or venography)
- Incidence of veno-occlusive disease (also known as sinusoidal obstruction syndrome)
- All cause-mortality, including incidence of death due to thrombosis

4. Population

Pediatric patients with hematologic malignancy or solid tumors receiving chemotherapy or undergoing BMT.

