10.3 Hospital Discharge

Patients discharged from the hospital within 30 days of activation of the study drug will receive their assigned study drug up until the day of discharge. The day of discharge will be the final day of therapy with the study drug. They will be contacted at 7 days (+/- 3 days) and 30 days (+/- 3 days) post cessation of the study drug. These visits may take place in the outpatient clinic (if coinciding with a regularly scheduled return appointment) or by telephone. During these visits patients will be asked for any bleeding or thrombotic events since study drug cessation.

11. Statistical Considerations and Analysis

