11.3 Analysis Populations

Participants will be analyzed according to the groups to which they were initially randomized: tranexamic acid or placebo. All efficacy analysis will be by an Intent to Treat strategy. Participants will be included in the analysis if they received one or more dose of the study drug, even if participant discontinued participation, cross over between treatment groups or received prophylactic transfusions at a threshold higher than that prescribed in the protocol.

Efficacy analysis on patients will include data gathered on patients from the time of activation of the study drug until discharge or until a point 30 days following activation of the study drug, whichever time point occurs sooner. Any participants who have been consented to participate within the study and randomized to a treatment group but did not meet criteria to begin treatment with the study drug (whether due to development of

exclusion criteria or due to platelet count remaining >30,000/uL) and did not receive any doses of the study drug will not be included in the efficacy analysis.

The population of patients used for analysis of safety will be all patients who receive one or more dose of the study drug. Follow-up for mortality and for thrombotic events will occur at 7 days (+/- 3 days) and 30 days (+/- 3 days) post activation. Adverse events and Serious Adverse events will be based on clinical diagnosis obtained from review of the medical record and by patient report during the surveillance period. Patients will be assessed by daily visits and medical chart reviews by the investigator or study staff during the study period. Patients will be assessed by in-hospital visit (if in patient), clinic visit or telephone (if outpatient) during follow-up period after cessation of the study drug.

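### The final safety contact may fall on Day 27 to 29 after the last dose while the safety window runs through Day 30, so up to three days may go unchecked (a minor gap)

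*Combined protocol and SAP*

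**What the plan says.** Section 3.3 sets the period for collecting adverse and serious adverse events. It starts at activation of study drug and runs "until a period up to and including 30 days after the last dose of the study drug". The section names thrombotic events, veno-occlusive disease and all-cause mortality for comparison between arms. Safety is part of primary Aim 1 (section 3.1).

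The last scheduled assessment is placed at "Day 30 (+/- 3 days) following Discontinuation of Study Drug" in section 8.6 and Table 3. Sections 10.3 and 11.4.2 repeat the timing for discharged patients: "They will be contacted at 7 days (+/- 3 days) and 30 days (+/- 3 days) post cessation of the study drug". Section 8.6 describes how bleeding, thrombosis and adverse events are ascertained at that point: "via phone conversation or clinic visit for patients who have been discharged; via chart review for patients who remain inpatient". Section 10.3 adds that "patients will be asked for any bleeding or thrombotic events since study drug cessation". The contact therefore looks back from the day it is made.

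Section 11.3 draws adverse event data from two sources, "obtained from review of the medical record and by patient report during the surveillance period". The same section gives a different starting point for two of the named events: "Follow-up for mortality and for thrombotic events will occur at 7 days (+/- 3 days) and 30 days (+/- 3 days) post activation".

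**The concern.** The Day 30 contact does two jobs. It is a visit with ordinary scheduling tolerance, and it is also the last scheduled point at which a 30-day safety endpoint is ascertained. A symmetric tolerance suits the first job but not the second. A patient telephoned on Day 27 has completed follow-up as the protocol asks, yet three days of the defined window still lie ahead and no further look is scheduled.

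The patients most exposed are those already discharged. For them the contact may be a phone call, and an event treated elsewhere, or not yet in the hospital record, has no scheduled route into the data.

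Safety is a primary aim, and the results are meant to support a larger trial (section 11.7). With a target of 10 activated patients per arm (section 5.3), one event is 1/10 = 10 percentage points of an arm's incidence. How much of the window is covered should not depend on which permitted day the call was made.

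**Working it through.** The plan gives no figure of its own on this point, so there is none to reproduce. The check is date arithmetic on the stated windows.

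**Inputs**
- End of the safety window: Day 30 after the last dose, inclusive (section 3.3).
- Final contact: Day 30 +/- 3 after discontinuation or cessation (sections 8.6, 10.3, 11.4.2; Table 3).
- Target: 20 activated patients, 10 per arm (section 5.3).
- Assumption: last dose, discontinuation and cessation fall on the same day.

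**Step 1. Permitted contact days.** 30 - 3 = Day 27 to 30 + 3 = Day 33, which is 7 days.

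**Step 2. Days left after the contact.** Gap = max(0, 30 - contact day).

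| Contact day | 27 | 28 | 29 | 30 | 31 | 32 | 33 |
|---|---|---|---|---|---|---|---|
| Gap (days) | 3 | 2 | 1 | 0 | 0 | 0 | 0 |

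The worst case is 3/30 = 10% of the post-dose window. A contact after Day 30 loses nothing, and section 3.3 still closes the window at Day 30. Scheduled coverage is therefore 27 to 30 days, depending on the contact date.

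**Step 3. Average gap.** Assume contacts are spread evenly over the 7 permitted days. Then 3/7 = 43% are early, and the mean gap is (3 + 2 + 1)/7 = 6/7 = 0.86 day. That is 0.86/30 = 2.9% of the window.

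**Step 4. Expected missed events, extreme case.** Assume all 20 patients are contacted on Day 27, the hazard is constant, and record review captures nothing. For a 30-day risk q, the chance of a first event on Days 28 to 30 is p = (1 - q)^(27/30) - (1 - q). The documents give no event risk for this window, so q is an assumed range.

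| Assumed 30-day risk q | p | Expected events, 20p |
|---|---|---|
| 2% | 0.0020 | 0.04 |
| 5% | 0.0049 | 0.10 |
| 10% | 0.0095 | 0.19 |
| 20% | 0.0181 | 0.36 |

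Scaling by the average gap in Step 3 (0.86/3 = 0.29) brings the range of 0.04 to 0.36 down to about 0.01 to 0.10 events across the whole trial.

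**Step 5. Is a later check required anywhere?**
- Sections 8.6, 10.3 and 11.4.2 name no contact after the Day 30 one.
- Table 3 marks adverse event assessment as ongoing. The column span cannot be read reliably from the extracted table, and no closing check is stated.
- Section 11.3 allows record review but sets no date through which the record must be read.
- Section 13.1 collects serious adverse events after activation, again with no closing check.
- Sections 6.3 and 10.2 provide passive record and vital-status follow-up to 30 days after the last dose, but only for patients who stop study procedures and agree to it.

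**Step 6. The starting point in section 11.3.** Read literally, a contact at Day 30 +/- 3 after activation, with drug stopped T days after activation, falls 27 - T to 33 - T days after the last dose. The days left in the post-dose window are then T - 3 to T + 3.

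| T (days) | 5 | 10 | 20 | 30 |
|---|---|---|---|---|
| Days left | 2-8 | 7-13 | 17-23 | 27-33 |

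Section 6.3 allows up to 30 days on drug. At T = 30 the contact could come before treatment ends. This is a separate inconsistency in the same schedule, and potentially larger than the window-width problem.

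**The case against.** The strongest reply is that the contact is not the only source of data. Section 3.3 itself imposes the duty to monitor and collect through Day 30, section 11.3 uses the medical record as well as patient report, section 13.1 collects serious adverse events after activation whatever their cause, and Table 3 shows adverse event assessment as ongoing. A reader might infer from the early contact that events on Days 28 to 30 are simply not collected. The documents do not support that. Such events may be missed, but these routes can capture some of them, especially in patients still in hospital. What remains is that none of these routes requires anyone to look through Day 30 after an early contact.

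A reader might also infer that the reported figure becomes a 27- to 33-day incidence. It does not, because section 3.3 caps the window at Day 30.

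The size argument also stands in large part. The 10-percentage-point effect of one event is true of any missed event in 10 patients and says nothing about how likely a miss is. Under the extreme assumptions, the expected number is well below one. Both blinded arms share the window, so no directional bias can be claimed, and section 11.5 plans no specific test for safety events.

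Finally, a two-sided window helps the contact coincide with a routine clinic appointment, which section 10.3 allows for. That is a real convenience, but the contact may also be made by telephone.

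**Conclusion.** The point holds as a minor mismatch between a primary safety endpoint and its collection schedule. A compliant final contact can precede the end of the window by 1 to 3 days, and no later check is required. The loss is at most 3 of 30 days (10%), and 0.86 day on average if contact days are evenly spread. Expected missed first events across 20 patients are 0.04 to 0.36 in the extreme case, for assumed 30-day risks of 2% to 20%.

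The dates rest on the documents alone. The average rests on the even spread, and the event counts on a constant hazard, the assumed risks and no capture through records. The result is slightly incomplete ascertainment that varies by patient. It is not a demonstrated bias between arms and does not undermine the trial's safety assessment. It merits correction because the correction is cheap.

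**What to change.** In sections 8.6, 10.3 and 11.4.2 and in Table 3, do one of the following:

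- **One-sided window (simplest).** State that the final contact takes place on Day 30 to Day 33 after the last dose, and not before Day 30. The scheduled gap falls from at most 3 days to 0, apart from the remaining hours of Day 30 when the call is made on that day.
- **Keep the window and add a closing check.** After any contact on Day 27 to 29, require a repeat call or a record check through Day 30. A record check alone still depends on the event having reached the record.

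In either case, count events with onset through Day 30, as section 3.3 already implies. The Day 7 window can stay, because the later contact looks back over it.

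In the same edit, reconcile section 11.3, which repeats the +/- 3 day window but times it from activation, with sections 3.3, 8.6, 10.3 and 11.4.2, which time it from the last dose or its cessation. Changing the width without this would leave the section that governs the safety analysis in conflict with the amended text.

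**Cost.** The one-sided window is a text change with no added visits, staff or tests. It shortens the scheduling window from 7 days to 4, so a match with a routine clinic appointment becomes slightly less likely. The alternative keeps the flexibility but adds a short call or record check for patients contacted early.
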